8.2 Randomisation Procedures

Participant randomisation will be undertaken centrally by the coordinating trial team using a web based system called Sealed Envelope

Following participant consent, and confirmation of eligibility (see section 8.1 for pre-treatment assessments), the randomisation procedure described below will be carried out.

A research assistant who is not involved in the study will enter the patient's trial ID into the web based randomization system ("sealed Envelope"). This system will randomly allocate the participant to either the intervention or control arm. He/she will inform the participants (carers/ individuals with dementia) of their allocation and will inform a relevant member of the research team. The randomisation list will be kept online.

In order to ensure that randomization is concealed, the professionals referring the participant, the participants at the time of enrollment and the research team will have no knowledge of the allocation prior to the start of the intervention. It will not be possible to blind the participants to the allocation group. However, the research assistant administering the questionnaires will be blind to the allocation group. At the end of the study we will assess researcher blindness by asking them to guess the allocated group.

Participants are considered to be enrolled into the trial following: consent, pre-treatment assessments (see section 8.1), confirmation of eligibility, completion of the randomisation process, allocation of the participant trial number and intervention by the central coordinating team.

8.3 Intervention procedures

The intervention will be delivered by the carer of the individual with dementia and will take place at home. Carers will attend a one day training session either in a group setting or individual training at home, depending on their preference, which will be provided by the research team. They will receive training on how to use the adapted manual and will receive a copy of the adapted manual, a workbook and additional materials (e.g. deck cards and dominoes).

The intervention will comprise of 40 sessions of individual Cognitive Stimulation Therapy (CST). Each carer will administer the activities within the manual two times a week for 30 minutes, over a period of 20 weeks. The activities will be tailored to the ability and interests of the individual with ID. Carers will be asked to keep a record of their session (e.g. how long, type of activities and reasons for not competing the session) in a diary.

If a carer is unable to continue the intervention (e.g. due to poor health) then another carer can be substituted. In order to support the carers and to ensure continued momentum, a member of the research team (clinical psychology trainee) will provide ongoing support to carers during the trial, and will address difficulties that carers may have in implementing the intervention. He/she will visit each dyad at least once a month and will telephone and email in between visits. The intervention group will also have access to "usual care" and therefore the intervention arm will be examining the additional effects of individual CST.

8.4 Subsequent assessments and procedures

The following measures will be administered at 10 weeks and 21 weeks at the participants' homes. See section on pre-intervention assessments for further information about the measures.

- 1. Cambridge Cognitive Examination (CAMCOG-DS)
- 2. Memory for Objects test from the Neuropsychological Assessment of Dementia in Intellectual Disabilities Battery.
- 3. The Cognitive Scale for Down Syndrome (CS-DS).
- 4. Activities of Daily Living Inventory (ADCS-ADL).
- 5. QOL-AD

All the carers will also be asked to complete the following measures:

- 1. Care Giving Burden Scale
- 2. Sense of competence in Dementia Care Staff (CSIDS) Scale
- 3. Hospital Anxiety and Depression Scale (HADS).

In order to assess adherence to the manual, for each dyad, two sessions will be audio-recorded (40 sessions in total). A brief adherence measure will be developed for the study.

At the end of intervention all the participants will be given a short questionnaire to complete about their experience of participating in the study, including feedback about whether they thought the intervention was practical and acceptable, such as whether the number of sessions were appropriate.

Ten carers and ten individuals with ID will be invited (5 carers and 5 individuals from each group) to participate in a semi-structured interview where more detailed feedback will be obtained about the study in general, including the study procedures. For those in the intervention arm, we will obtain feedback about the different components of the intervention such as the training given to carers and views about the iCST manual. We will ask about what aspects of the intervention worked or did not work well and what improvements could be made.

A schedule of all trial assessments and procedures is set-out in Appendix 1.

Payment

Gift vouchers will be given to all participants in the study to thank them for their time and for the inconvenience caused by taking part in the study. In the control arm, the carers and participants with dementia will receive a £10 gift voucher for completing each follow up assessment (at 11 weeks and 21 weeks).

The carers (both paid and informal) in the intervention arm will receive a £10 gift voucher after completing each follow up assessment, and a further £10 for completing each audio-taped session (total of £40). The participants with dementia will receive a £10 gift voucher after completing each assessment.

The carers and individuals with ID that volunteer to participate in the semi-structured interview at the end of the trial will receive a £10 gift voucher.

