11.2 Secondary outcome(s)

For all the secondary outcomes, we will explore changes in the mean scores and standard deviation pre and post intervention in each group, as well as between group differences.

- 1. Cognitive functioning measured using the memory for Objects test. This is a continuous measure.
- 2. Cognitive functioning measured using the CS-DS. This is a continuous measure.
- 3. Adaptive functioning will be measured using the ADCS-ADL. This is a continuous measure.
- 4. Quality of Life will be measured using the QOL-AD. This is a continuous measure.
- 5. Care giving burden will be assessed using the care Giving Burden Scale. This is a continuous measure.
- 6. The competence of dementia staff will be measured using the SCIDS. This is a continuous measure.
- 7. Anxiety and depression in carers will be measured using the Hospital Anxiety and Depression Scale. This is a continuous measure.

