11.6.3 Secondary outcome analysis

As this is a feasibility study, we do not anticipate that there will be a statistically significant difference between the two groups in relation to the secondary outcomes. For each of the secondary outcomes, changes in the mean and standard deviation between the two groups will be calculated using Analysis of Covariance (ANCOVA), adjusting for the baseline score on the secondary outcome measure.

Other analyses:

The 40 recorded iCST sessions will be independently assessed by two raters for adherence to the manual. We will examine the carers' diaries to calculate the mean number of sessions that were completed by the carers and reasons for non-completion.

The qualitative interviews will be transcribed and analysed using thematic analysis to identify recurrent themes concerning participants' perceptions of the intervention. The findings will be used to further modify the intervention and to revise the manual.

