Appendix 1 - Schedule of assessments

	Screening (pre- treatment assessment)	Intervention phase			Final visit	Optional	
Visit No:	1	2	3	4	5	6	7
		Week 1	Week 5	Week 11	Week 15	Week 20	
Window of flexibility for timing of visits:			e.g.+/- 7 days	E.g+/- 7 days		e.g.+/- 7 days	
Informed Consent	x						
Medical History	Х						
Eligibility confirmation (ICD- 10 criteria)	х						
CAMCOG-DS	х			х		х	
Memory for Objects Test	х			X		x	
CSDS	х			X		x	
ADCS-ADL	x			X		x	
QOL-AD	x			X		x	
Care giver burden scale	x			х		x	
HADS	x			х		x	
SCIDS Scale	х						
Training for carers		Х					
Treatment adherence/monitoring visit			Х		х		
Trial evaluation questionnaire						х	
Semi-structured interview							Х
Randomisation	Х						
Adverse Events review	X	X		X		X	
Concomitant Medication review	late version 1 (3	0/11/2015) X		х		х

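### The protocol text repeats the SCIDS at both follow-ups and plans a baseline-adjusted comparison of it, but Appendix 1 schedules it at screening only

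*Protocol*

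**What the plan says.** Four parts of the protocol body treat the SCIDS as a repeated measure.

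- Section 8.1 has all carers complete it before randomisation. It is a 17-item scale with a maximum of 68, to be lightly reworded so that it also suits family members.
- Section 8.4 opens its list of follow-up measures with "The following measures will be administered at 10 weeks and 21 weeks", and the carer part of that list contains "Sense of competence in Dementia Care Staff (CSIDS) Scale". The acronym has two letters transposed, but it is clearly the same scale.
- Section 11.2 gives it as secondary outcome 6: "The competence of dementia staff will be measured using the SCIDS. This is a continuous measure". For all secondary outcomes the same section says "we will explore changes in the mean scores and standard deviation pre and post intervention in each group, as well as between group differences".
- Section 11.6.3 sets the analysis for each secondary outcome: "changes in the mean and standard deviation between the two groups will be calculated using Analysis of Covariance (ANCOVA), adjusting for the baseline score".

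Appendix 1 differs. Its SCIDS row has a single mark, in the screening column. The row for another carer measure, "Care giver burden scale", has three marks: screening, week 11 and the final visit. Section 8.4 directs the reader to this table: "A schedule of all trial assessments and procedures is set-out in Appendix 1".

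**The concern.** A schedule of assessments is commonly what visit packs and CRFs are built from, and 8.4 itself points to it. Someone preparing the week 11 or final visit from Appendix 1 would leave the SCIDS out. A carer score not taken at its visit cannot be recovered later, and no analysis plan can supply it.

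The SCIDS is the only listed measure of carer competence, in a trial where carers are trained to deliver the intervention. Secondary objective 1 also asks whether the outcome measures are suitable, and this scale is being adapted for a group it was not developed for. Its behaviour over time is therefore useful information for the larger trial.

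**Working it through.** The protocol attaches no figure to this point, so the check is a cross-reading and a count.

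**Step 1. Times each source has the SCIDS administered.**

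| Source | Baseline | First follow-up | Second follow-up | Total |
|---|---|---|---|---|
| Sections 8.1 and 8.4 | 1 | 1 | 1 | 3 |
| Appendix 1 | 1 | 0 | 0 | 1 |

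The two sources differ by 3 - 1 = 2 administrations per carer, both after baseline.

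**Step 2. The other rows of Appendix 1.** CAMCOG-DS, Memory for Objects, CS-DS, ADCS-ADL, QOL-AD, the caregiver burden scale and HADS each have three marks, at screening, week 11 and the final visit. That is 7 x 3 = 21 marks. With the single SCIDS mark the table holds 22, whereas 8.1 and 8.4 together imply 8 x 3 = 24. The two missing marks are both in the SCIDS row.

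**Step 3. Could the marks have been lost in reading the PDF?** It is possible but unlikely. All seven other outcome rows, including HADS directly above, keep their three marks. The final row of the table is visibly damaged by footer text, but the SCIDS row is not.

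**Step 4. What the planned analysis needs.** A change is follow-up score minus baseline score. A baseline-adjusted ANCOVA regresses a post-baseline quantity (the follow-up score or the change) on arm and baseline score. Both need at least one post-baseline value per carer. Under Appendix 1 the number available is 0 of 20 in each arm, so neither can be computed.

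**Step 5. Size.** With the planned 40 dyads and two follow-ups, the maximum loss is 2 x 40 = 80 forms, which is all follow-up data for 1 of 7 secondary outcomes and 1 of 3 carer measures. If a proportion p of the visits is run from Appendix 1, the loss is 80p. The protocol gives no basis for p, so the range is 0 (everyone uses 8.4) to 80 (everyone uses Appendix 1). The upper end assumes full recruitment and no dropout.

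The follow-up weeks also differ between the sources: 10 and 21 weeks in 8.4, weeks 11 and 20 in Appendix 1. That is a separate matter. Under either labelling there are two follow-up visits, and Appendix 1 has no SCIDS at either.

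**The case against.** The strongest reply is that the intention is plain. Sections 8.4, 11.2 and 11.6.3 agree with one another and only one table row disagrees, so this looks like a clerical slip and not a design decision. Staff who work from 8.4 will collect the scale. This stands, and it is why the point is classed as an inconsistency. It does not remove the need for correction, because nothing in the protocol says which text prevails.

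Three stronger readings are tempting, and the document does not support them.

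- A reader might infer that the between-arm analysis of the SCIDS is already impossible. That is so only where Appendix 1 is followed in preference to 8.4. No CRF is shown, and the sentence pointing to the appendix does not rank it above the body text.
- A reader might infer that the trial could not judge the SCIDS as an outcome measure at all. Baseline administration is scheduled in both sources. It would show completion, missing items, floor and ceiling effects, and how the reworded items work with family carers. What would be lost is completion at follow-up, change, and the between-arm estimate.
- A reader might infer that missing data will differ by site. Sections 8.2 and 9.6 speak of a single research assistant administering the questionnaires, which suggests central assessment, while 10.3 has delegated staff completing CRFs with copies kept at site. Site differences are possible, but nothing shows that they are likely.

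The stakes are also limited. This is a feasibility trial without a power calculation. The CAMCOG-DS, the recruitment, retention and adherence data, and the standard deviation wanted for the larger trial are all unaffected.

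**Conclusion.** The contradiction is real, and its severity is moderate. Three concordant sections require the SCIDS at two follow-ups, and Appendix 1 schedules it at neither. Between 0 and 80 follow-up forms are at risk, depending on which text staff and CRF packs follow. Where Appendix 1 is followed, secondary outcome 6 is reduced to a baseline description.

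The conclusion rests on two assumptions: that the SCIDS row of the table has been read correctly, which the intact neighbouring rows support, and that at least some visits or CRF packs are prepared from the schedule. It does not extend to the primary outcome or to the feasibility measures.

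**What to change.** In Appendix 1, mark the SCIDS at the week 11 visit and the final visit, as is already done for HADS and the Care Giving Burden Scale. Include it in the CRF packs for both visits, ideally before the first follow-up takes place. Correct the transposed acronym in 8.4 at the same time.

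The cost is two marks in a table and one 17-item form per carer at each of two visits. Section 8.1 allows up to two hours with the carer at baseline and at later assessments, and the SCIDS is already among the carer measures listed there, so no extra session time is needed.

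Deleting the SCIDS from 8.4 and from the follow-up analysis in 11.2 and 11.6.3 would also make the document consistent. However, it would go against three sections that agree and would give up the only measure of carer competence over time.

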A group at UCL, led by [name], have developed a manualised individual CST (iCST) intervention for people with dementia (without ID (13, 14). They have recently completed a multicentre randomised controlled trial of iCST delivered by family carers, compared to "treatment as usual" in 356 carers and individuals with dementia (15). The intervention comprises 75 sessions (each session was 30 minutes, given 3 times a week, over 25 weeks). This study found that iCST did not improve cognition or quality of life for people with dementia and it did not improve carers' physical or mental health. However, there was some improvement in the caregiving relationship and in carers' health related quality of life. Possible reasons for the lack of differences in the treatment and control groups in relation to cognition and quality of life could be attributed to the poor compliance rate. Only 51% of the dyads completed more than 30 sessions out of 75 and 22% did not complete any sessions. Adherence analyses found that people with dementia who completed more sessions showed improved quality in the caregiving relationship and carers reported lower depressive symptoms at 26 weeks. Qualitative data suggested that people with dementia and their carers experienced better communication as a result of iCST.

No studies have examined the feasibility of individual CST in people with ID with or without dementia. We aim to work closely with our UCL colleagues in developing individual CST for people with ID and dementia.

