8.6 Discontinuation/withdrawal of participants

A participant may be withdrawn from trial whenever continued participation is no longer in the participant's best interests, but the reasons for doing so must be recorded. Reasons for discontinuing the trial may include:

disease progression whilst on therapy

- intercurrent illness
- patients withdrawing consent or Personal/Nominated Consultees withdrawing assent for participants lacking capacity
- persistent non-compliance to protocol requirements.

The decision to withdraw a participant from treatment will be recorded in the CRF and medical notes. If a participant explicitly states they do not wish to contribute further data to the trial their decision must be respected and recorded in the CRF and medical notes.

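### Dyads that leave before the final visit give no acceptability rating, so the acceptability result is likely to be too favourable

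*Protocol*

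**What the plan says.** Section 4 makes tolerability and acceptability of iCST an objective of the randomised phase, to be judged from several indicators that include drop-out and adherence.

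Acceptability is asked about directly in two places:

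- **Questionnaire.** Section 8.4: "At the end of intervention all the participants will be given a short questionnaire to complete about their experience of participating in the study". The same sentence says that it covers whether the intervention was practical and acceptable, and gives the number of sessions as an example. In Appendix 1 the row "Trial evaluation questionnaire" is marked at one visit only, the final visit (week 20 in that table).
- **Interviews.** Section 8.4: "Ten carers and ten individuals with ID will be invited (5 carers and 5 individuals from each group) to participate in a semi-structured interview". The payment text of the same section describes the interviewees as those "that volunteer to participate in the semi-structured interview at the end of the trial". Neither passage says how interviewees are chosen with respect to adherence.

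Section 8.6 lists disease progression and "persistent non-compliance to protocol requirements" among possible reasons for discontinuing the trial. It requires a record of why a participant is withdrawn ("but the reasons for doing so must be recorded") but mentions no exit questionnaire or exit call. It does not say whether a dyad that stops iCST stays in follow-up.

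Section 11.6.3 adds an analysis of the carers' diaries, giving the mean number of sessions done and why sessions were not completed. It also says that the interview findings will be used to revise the manual.

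**The concern.** A dyad that finds iCST impractical or unpleasant is more likely than others to stop. If it also leaves the trial, it is gone before the one occasion on which its opinion would be asked. Ratings then come from those who remained, and the manual is revised on interviews that need not include anyone who stopped.

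The protocol's own background shows that this is foreseeable. Section 3 reports that in the completed iCST trial in people without ID, "22% did not complete any sessions" and only 51% of dyads did more than 30 of 75. It offers poor compliance as a possible reason for that trial's lack of effect on cognition and quality of life. Why dyads stop, and what they thought of the intervention, is therefore something this feasibility trial should learn. These views are hard to recover once a dyad has gone.

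A smaller point concerns the control arm. The questionnaire sentence covers all participants, yet section 7.1 gives controls usual care only and offers them the manual at the end of the study. For the interviews, section 8.4 limits questions about the intervention to the iCST arm. It sets no such limit for the questionnaire.

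**Working it through.** The protocol gives no acceptability estimate, drop-out rate or threshold, so there is no figure to reproduce. The check has two parts.

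**1. Who is reached, reading the sections together**

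| Situation of an iCST dyad | Final-visit questionnaire | Interview | Other information |
|---|---|---|---|
| Completes iCST | Yes | Possible | Diary |
| Stops iCST, stays in follow-up | Yes, on the wording of 8.4 | Possible, not assured | Diary reasons for uncompleted sessions |
| Leaves the trial before the final visit | No stated route | No stated route | Recorded withdrawal reason; diary up to leaving |

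The gap is the third row. How many dyads fall there rather than in the second row depends on a point that section 8.6 leaves open.

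**2. How much it could matter (illustration only)**

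Inputs:
- 20 iCST dyads (section 8.4 and the trial design in section 5 both imply 20 per arm).
- *d*, the share not reached by the questionnaire. It is not given. 22% is borrowed from section 3, where it is the share that completed no session in another trial, not a rate of leaving. On 20 dyads it is 0.22 × 20 = 4.4. The range shown is 10% to 49%, where 49% = 100% − 51%, the share in that trial that did not exceed 30 sessions.
- *p*r, the approval rate among respondents: assumed 80%.
- *p*m, the approval rate among those missed: assumed 0% to 50%, and 80% for no difference.

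Formulas: all-dyad approval = (1 − *d*)·*p*r + *d*·*p*m, and overstatement = *d*·(*p*r − *p*m).

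With *d* = 22%:
- *p*m = 0%: 0.78 × 0.80 + 0.22 × 0 = 0.624, overstatement 17.6 points
- *p*m = 20%: 0.624 + 0.22 × 0.20 = 0.668, overstatement 13.2 points
- *p*m = 50%: 0.624 + 0.22 × 0.50 = 0.734, overstatement 6.6 points
- *p*m = 80%: 0.624 + 0.22 × 0.80 = 0.800, overstatement 0

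For *p*m between 50% and 0%, the overstatement is 3 to 8 points with *d* = 10% and 14.7 to 39.2 points with *d* = 49%.

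As whole dyads: if 4 of 20 are not reached and 14 of the 16 respondents approve (88%), the all-dyad rate can lie anywhere from 14/20 = 70% to 18/20 = 90%.

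**The case against.** The strongest reply is that the questionnaire goes to all participants, not to completers. Withdrawal under section 8.6 is optional, and that section treats leaving treatment separately from refusing to give further data. Section 11.6.1 likewise counts completing the intervention apart from completing the final assessment. So a reader might infer that every dyad that gave up iCST goes unheard, and the text does not support that. A dyad that stops but stays is due the questionnaire. This part of the reply stands, and it limits the point to dyads that leave.

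A reader might also infer that reasons for stopping are lost. They are not. Withdrawal reasons must be recorded, diary reasons are analysed, and section 8.3 provides monthly support visits with contact in between. Drop-out and adherence are reported in their own right, so a favourable questionnaire would be read beside them. This also stands, but none of these sources is a rating of practicality or acceptability, and no support contact is assigned to collect one.

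On the interviews, people are invited, any consented interview is voluntary, and nothing excludes dyads that stopped. That is fair. The weakness is only that nothing ensures their inclusion among five carers and five individuals in the iCST arm.

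On the control arm, the questionnaire is not shown, and controls can answer about taking part. The text merely leaves open whether they also get the intervention items.

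**Conclusion.** The point holds as a risk. As written, the protocol gives no route for an acceptability rating from a dyad that leaves before the final visit, and no rule brings dyads that stopped into the interviews. The likely direction is too favourable, because dislike or impracticality is one reason to leave.

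It would go too far to state upward bias as a fact. The protocol gives neither the share that will leave nor their views, and a dyad that leaves because of illness or progression may have valued iCST. The shift is zero if those missed think like those who stay, or if everyone is still reached at the final visit.

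The range of 62% to 73% against 80% rests on three assumptions: 22% not reached, 80% approval among respondents, and 0% to 50% among those missed. It is not a forecast. The 22% comes from a trial with family carers and three sessions a week, whereas this one allows paid carers and plans two sessions a week. The protocol also does not commit to reporting an acceptability percentage.

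The change is worth making because it is cheap and must be in place before dyads leave.

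**What to change.** In section 8.4 and Appendix 1:

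1. Offer the evaluation questionnaire also at the time a dyad stops iCST or leaves the trial, with consent, by phone or post. State that dyads that stopped iCST but remain in follow-up also receive it at the final visit.
2. Invite some of the already planned iCST-arm interviewees from dyads that stopped or completed few sessions, if there are any.
3. Put the items on practicality, acceptability and number of sessions to the iCST arm only, as section 8.4 already does for the interviews. Controls would answer the items on taking part in the study.

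The choice of denominator and the handling of non-responders can be left to the statistical analysis plan.

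Cost: a few short calls or postings, with no added visits and no more interviews than planned. Some who leave will decline, so the gap will narrow but may not close.
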